7.3.7. Pregnancy Testing and Reporting

The need for a screening pregnancy test depends on whether a female subject is of childbearing potential or non-childbearing potential.

If a female subject is of childbearing potential, she must have a serum β -HCG pregnancy test performed within 7 days prior to the first dose of study treatment. Subjects with positive pregnancy test result must be excluded from the study. Subjects with negative pregnancy test result must agree to use an effective contraception method as described in Section 10.1 during the study until at least 2 weeks (14 days) after permanent discontinuation of study treatment.

Any pregnancy that occurs during study participation must be reported using a clinical trial pregnancy notification and follow –up form. To ensure subject safety, each pregnancy must be reported to GSK within 2 weeks of learning of its occurrence. The pregnancy must be followed up to determine outcome (including premature termination) and status of mother and child. While pregnancy itself is not considered to be an AE or SAE, pregnancy complications and elective terminations for medical reasons must be reported as an AE or SAE. Spontaneous abortions must be reported as an SAE.

Any SAE occurring in association with a pregnancy brought to the investigator's attention after the subject has completed the study and considered by the investigator as possibly related to the study treatments, must be promptly reported to GSK.

Any female subject who becomes pregnant while participating in the study will be withdrawn from the study. Study treatment should be immediately withdrawn from a subject who becomes pregnant during the study in order to eliminate further exposure of the embryo to the study treatment.

In addition, the investigator must attempt to collect pregnancy information on any female partners of male study subjects who become pregnant while the subject is enrolled in the study. Pregnancy information must be reported to GSK as described above.

7.4. Pharmacokinetics

7.4.1. Blood Sample Collection for Pharmacokinetics

Blood samples for PK analysis of GSK2816126 will be collected at the time points indicated in the Time and Events Schedule (Section 7.1). Some of the blood drawn may be used to produce dry blood matrix samples at the same time points. Each PK sample should be collected as close as possible to the planned time relative to the dose (i.e., time zero) administered to the subject on PK days. The actual date and time of each blood sample collection will be recorded. The timing of PK samples may be altered and/or PK samples may be obtained at additional time points to ensure thorough PK monitoring. This would not require a protocol amendment.

Subjects participating in the Part 2 PK/PD expansion cohort, additional blood samples will be collected for metabolite profiling.

Details on PK blood sample and dry blood matrix sample collection, processing, storage and shipping procedures are provided in the SPM.

7.4.2. Bile Sample Collection for Pharmacokinetics

Subjects participating in the Part2 PK/PD expansion cohort, bile samples for analysis of GSK2816126 and its metabolites may be collected via the Entero-Test [Guiney, 2011] over the time period specified in the Time and Events Table (see Section 7.1).

Full details of the Entero-Test sample collection, processing, storage and shipping procedures are provided in the SPM.

7.4.3. Urine Sample Collection for Pharmacokinetics

Urine may be collected for metabolic profiling in subjects in the PK/PD expansion cohort of Part 2 at the time points indicated in the Time and Events Schedule (Section 7.1).

7.4.4. Plasma Sample for CYP3A4 Enzyme Activity

Plasma collected in the Part 2 PK/PD expansion cohort may be analyzed for 4 β -hydroxycholesterol (as well as cholesterol) as a potential in vivo marker of CYP3A4 enzyme activity and the results will be reported under a separate Mechanistic Safety and Disposition protocol. Samples collected pre-treatment and at steady-state will be compared to evaluate this potential biomarker.

Details on CYP3A4 enzyme activity marker plasma sample collection, processing, storage and shipping procedures are provided in the SPM.

7.4.5. Pharmacokinetic Sample Analysis

Blood sample analysis will be performed under the management of Bioanalysis Immunogenicity and Biomarker, In Vitro In Vivo Translation , Platform Technology and Science, GSK. Concentrations of GSK2816126 will be determined in blood samples using the most current approved and validated analytical methodology. Blood raw data will be stored in the Good Laboratory Practices (GLP) Archives, GSK. Once the blood has been analyzed for GSK2816126, any remaining blood may be analyzed qualitatively for circulating metabolites and the results reported under a separate drug metabolism and pharmacokinetics (DMPK) protocol.

If dry blood matrix samples are collected, they will be analyzed under the management of Bioanalysis Immunogenicity and Biomarker, *In Vitro In Vivo Translation* , Platform Technology and Science, GSK. Concentrations of GSK2816126 will be determined in dry blood matrix samples using a validated analytical methodology. Dried blood matrix raw data will be stored in the Good Laboratory Practices (GLP) Archives, GSK.

Urine sample analysis may be performed under the management of Bioanalysis, Immunogenicity and Biomarker, *In Vitro In Vivo Translation* , Platform Technology and Science, GSK. Concentrations of GSK2816126 may be determined in urine samples using an investigative analytical methodology. Urine raw data will be stored in the GLP Archives, GSK.

The urine and bile samples may be analyzed for compound-related metabolites and the results will be reported under a separate protocol.

Plasma analysis for 4 β -hydroxycholesterol and cholesterol may be conducted and the results reported under a separate protocol.

7.5. Pharmacodynamics

Changes from baseline H3K27me3 will be assessed in pre- and post-treatment samples for tumor or surrogate tissue/body fluid [e.g. Peripheral blood mononuclear cell (PBMCs), blood, skin or hair].

7.6. Translational Research

Translational or biomarker research may be performed on archival tissue, tumor biopsies, blood samples or other surrogate tissue (e.g. skin or hair) collected at various times throughout the study, to better understand the mechanism of action and response to GSK2816126. The successful collection of quality tissue specimens will be critical to furthering our understanding of EZH2 biology and identifying the best way to treat patients with an EZH2 inhibitor.

Comparative examination of pre-dosing profiles of participants may uncover known or novel candidate biomarkers/profiles which could be used to predict response to treatment with GSK2816126 or provide new insights into lymphoma, other cancers, and medically

related conditions. Comparative examination of post-dosing profiles in conjunction with pre-dosing profiles may yield known and novel candidate biomarkers/profiles and new insights which relate to the action of GSK2816126.

Performance of these investigations may be conditional on the results of the clinical trial principally, but not exclusively, on the primary measures of the clinical trial outcome and samples may be selected for analysis on the basis of the clinical outcome.

Unless stated otherwise, these investigations may be performed irrespective of whether a response to GSK2816126 is observed.

All samples may be retained for a maximum of 15 years after the last subject completes the trial.

Novel candidate biomarkers and subsequently discovered biomarkers of the biological response associated with lymphoma, or other cancers, and/or the action of GSK2816126 may be identified by application of DNA/gene, RNA and protein analysis of blood and tumor tissue including but not limited to the following analyses:

- Confirmation of GCB-subtype DLBCL status by IHC analysis using the standard methods or tumor Gene Expression Profile (GEP) signature
- Confirmation of EZH2 WT status by targeted sequencing of EZH2 gene
 - Subject tumors determined to be wild-type for the seven pre-defined EZH2 mutations assessed in the screening assay may be evaluated for the presence of additional, undefined, mutations in the EZH2 gene
- DNA analyses may be performed for somatic mutations in genes of interest (including, but not limited to, EZH2, UTX, BAP1, ARID1A, SMARCB1, SMARCA4, and PBRM1). Translocations including, but not limited to, BCL-2, BCL-6 and c-MYC, which have been observed in DLBCL, may also be assessed
- Circulating cell free-DNA (cfDNA) analysis of blood/plasma
- Circulating biomarker (DNA, RNA and/or protein) analysis of plasma
- RNA transcriptome analysis of blood and/or tissue samples.
- Measurement of the levels of a subset of RNA species in blood and/or tissue samples
- Analysis of protein expression by IHC or an alternative method may also be performed for proteins of interest.

7.6.1. Tumor Biomarker Analysis

To evaluate candidate biomarkers and identify novel predictors of sensitivity and/or resistance to GSK2816126, DNA, RNA or protein measurements will be assessed in archival tumor tissue or fresh biopsies. Specific tests, exploratory analyses and tissue requirements for each tumor type are indicated below and/or [Table 6](#).

7.6.1.1. GCB-DLBCL Subtyping (DLBCL subjects only)

Central confirmation of GCB DLBCL status will be confirmed by an IHC test utilizing the Choi algorithm [Choi, 2009] in Part 1 and 2.

Local testing, in advance of central confirmation may be performed to determine GCB status for enrollment using the Choi algorithm or a suitable alternative algorithm.

7.6.1.2. EZH2 Mutation Analysis (required for study entry in Part 2 for GCB-DLBCL and tFL subjects only)

Screening for eligibility for Part 2 of the study will be conducted using either an NGS-based gene panel or a custom quantitative real time polymerase chain reaction (RT-PCR) test based on TaqMan PCR chemistry. Both tests detect 7 known activating mutations in the EZH2 gene: Y641F (c.1937A>T); Y641N (c.1936T>A); Y641S (c.1937A>C); Y641H (c.1936T>C); Y641C (c.1937A>G); A677G (c.2045C>G); and A687V (c.2075C>T) .

EZH2 mutation analysis on archival tumor samples or fresh biopsies from subjects enrolled in Part 1 may also be performed, though the presence of an EZH2 mutation is not required for study entry in Part 1.

7.6.2. Circulating cell free DNA/RNA Analysis

Plasma samples may be analyzed to investigate mutations, including but not limited to EZH2, in cfDNA.

Tumor-specific circulating cell-free deoxyribonucleic acid (cfDNA) levels detected in plasma or serum have been found to correlate with increasing tumor burden and decline following therapy. Furthermore, cfDNA in cancer participants can harbor many genetic alterations (mutations, microsatellite alterations, aberrant methylation), which are generally consistent with the tumor. Additionally exosomes, released from tumor cells into circulation, which contain both DNA and RNA are increasingly being recognized as important source of cancer biomarkers. Thus, tumor-specific circulating cfDNA and exosomes have the potential to be a useful source of biomarkers of therapeutic response as well as offering a less invasive blood based technique for identifying and selecting participants for certain treatment. Methylation status of cfDNA may also be investigated.

7.6.3. Circulating biomarker analysis

Levels of circulating biomarkers may be assessed to determine relationships between biomarker expression and response to GSK2816126, as well as to better understand the expression of circulating biomarkers in lymphoma and other tumor types.

Biomarkers circulating in the plasma have been found to correlate with tumor pathway activation. Blood-based markers have the important advantage that specimens are readily available, simple to prepare and store, and can be taken prior to and during treatment. This allows for the assessment of predictive markers based on the baseline evaluation as

well as markers of activity and resistance based on changes that occur during treatment. Therefore, a broad panel of biomarkers may be evaluated in plasma and correlated with clinical outcome to treatment with GSK2816126.

7.6.4. RNA Expression Research

Transcriptional (RNA) analyses may be performed to better understand changes in gene expression profile upon treatment with GSK2816126 in tumor tissue and/or blood.

RNA expression studies may be conducted using RNA-seq, quantitative RT-PCR, and/or alternative equivalent technologies, which can facilitate the simultaneous measurement of the relative abundances of RNA species resulting in a RNA expression profile for each blood and tumor tissue sample. The RNAs assayed may be those involved in tumor pathogenesis, the absorption, distribution, metabolism, or excretion of GSK2816126, or in the subject's response to GSK2816126. In addition, continuing research may identify other proteins or regulatory RNAs that may be involved in response to GSK2816126 or tumor pathogenesis. The RNAs that code for these proteins and/or regulatory RNAs may also be studied. This will enable the evaluation of changes in RNA expression profiles that may correlate with biological response relating to specific cancers, and medically related conditions or the action of GSK2816126.

7.6.5. Tumor Tissue collection

Part 1:

- DLBCL subjects: the availability of archived tissue (or willingness to undergo fresh biopsy) is required for determination of EZH2 mutation status, and/or GCB-subtype.
- All other subjects: an archival tumor specimen (or willingness to undergo fresh biopsy) for retrospective DNA, RNA or protein testing of potential markers of sensitivity and/or resistance. Subjects for whom archived tissue is not available and biopsies are not feasible will be eligible for enrollment and participation in the study at the discretion of the GSK medical monitor. Contact GSK medical monitor for confirmation of enrollement and study entry if biopsies are not feasible.
- Pre and post treatment biopsies for PD and translational research activities are optional for all subjects.

Part 2:

- DLBCL cohorts: a fresh tumor biopsy is required for all screened subjects to determine EZH2 mutation status and GCB-subtype.
- tFL cohorts: a fresh tumor biopsy is required for all screened subjects to determine EZH2 mutation status.

- MM cohort: an archival tumor specimen or fresh tumor biopsy is required.
- PK/PD cohorts: Pre treatment and post treatment biopsies are required
- Pre and post treatment biopsies for PD and translational research activities are optional for all other subjects.

Retention of screen-failure tumor tissue: all or a portion of archival or fresh biopsy tissue from screen-failure subjects, used for central testing of GCB-DLBCL or EZH2 mutation status, will be retained. This tissue may be used in the validation of potential diagnostic assays to detect EZH2 mutations and/or for GCB-DLBCL subtyping.

A tumor biopsy at progression for biomarker research is recommended for all subjects.

Further details on sample requirements and collection will be provided in the SPM.

7.6.6. Blood collection

Blood samples will be collected at multiple time points from all subjects on study (Parts 1 and 2) for pharmacodynamic and exploratory biomarker testing (Section [7.1](#)).

A change in frequency of blood biomarker sampling times may be implemented based on emerging data. This would be determined by GSK and documented in formal communication to sites for implementation but would not require a protocol amendment..

Further details on sample requirements and collection will be provided in the SPM.

7.7. Evaluation of Anti-Cancer Activity

Disease assessment may include imaging and physical examination (as indicated for palpable/superficial lesions). Refer to [Appendix 4](#) for more details on response assessment criteria.

- Disease assessment for lymphomas will be completed within 4 weeks of first dose of GSK2816126 and repeated 8 weeks after dosing is initiated, every 12 weeks thereafter, and at the final study visit.
- Disease assessment for solid tumors will be completed within 4 weeks of first dose of GSK2816126 and repeated every 8 weeks after dosing is initiated, and at the final study visit.
- Disease assessment for MM will be completed within 4 weeks of first dose of GSK2816126, week 4 and repeated every 6 weeks thereafter.

See the Time and Events Table (Section [7.1](#)) for the schedule of assessments of anti-cancer activity. Assessments must be performed on a calendar schedule and should not be affected by dose interruptions/delays. For post-baseline assessments, a window of ± 7 days is permitted to allow for flexible scheduling. If the last radiographic assessment was more than 8 weeks prior to the subject's withdrawal from study and progressive

disease has not been documented, a disease assessment should be obtained at the time of withdrawal from study.

For subjects with NHL, the following B symptoms should be assessed at the time points in the Time and Events Table (Section 7.1):

- night sweats without signs of infection
- unintentional weight loss of $\geq 10\%$ within the previous 6 months
- recurrent, unexplained fever of greater than 38°C for 2 weeks without signs of infection

If a lymphoma subject had involvement of bone marrow at baseline, and a CR is suspected, a bone marrow biopsy must be obtained. A repeat bone marrow biopsy will be performed within 8 weeks of the imaging confirmed CR in accordance with the response guidelines. See [Appendix 4](#): Section 15.4 for additional details.

Tumor response will be assessed as outlined above and in the Time and Events Schedule by the investigator using:

- Lymphoma Subjects: Revised Response Criteria for Malignant Lymphoma (RRCLM)([Appendix 4](#))
- Solid Tumor RECIST 1.1 ([Appendix 5](#))
- Multiple Myeloma: International Myeloma Working Group (IMWG) ([Appendix 6](#))
- Prostate: RECIST 1.1 and PSA ([Appendix 7](#))

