6.3. Permanent Discontinuation from Study Treatment

Subjects will receive study treatment until disease progression, death or unacceptable toxicity, including meeting stopping criteria for liver chemistry defined in Section [8.3.1](#). In addition, study treatment will be permanently discontinued for any of the following reasons:

- Substantial deviation(s) from the protocol
- Request of the subject or proxy (withdrawal of consent by subject or proxy)
- Investigator's discretion
- A dose delay of >21days unless the investigator and GSK Medical Monitor agree that further treatment may benefit the subject
- Intercurrent illness that prevents further administration of study treatment(s)
- Subject is lost to follow-up
- Study is closed or terminated
- Female subject who becomes pregnant while on study treatment

The primary reason study treatment was permanently discontinued must be documented in the subject's medical records and eCRF.

If the subject voluntarily discontinues from treatment due to toxicity, 'adverse event' will be recorded as the primary reason for permanently discontinuation on the eCRF.

Once a subject has permanently discontinued from study treatment, the subject will not be allowed to be retreated.

All subjects who discontinue from study treatment will have safety/disease assessments at the post study treatment Follow Up Visit as specified in the Time and Events Tables.

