Tumor biopsy for PD optional for Part 1 and Part 2. Required for PK/PD cohort	A tumor biopsy should be obtained at D1 (up to -14 days) and after 6 th dose Day 18(+3 day window)		X		X (After 6 th dose, Day 18) ^h			
Tumor biopsy for biomarker research	Recommended for all subjects							X (at progression)
Additional Assessments for PD/PK Cohort ^m								
Blood for metabolite evaluation (Part 2 PK/PD expansion cohort only)			Day 1 (Table 7)		Day 15 (Table 7)			
Urine for Metabolite (Part 2 PK/PD expansion cohort only)	On Day 15, urine samples should be collected while subject is in the office		Day 1 prior to first dose and from 0 to 24h		Day 15 from 0 to 8 h			

	STUDY PHASE	SCREEN	First Treatment Period Cycle 1			Day 21	Continuation Phase Cycle 2 and beyond	Follow-Upⁱ
			Day 1 and 4^a	Day 8 and 11^a	Day 15 and 18^a			
	VISIT	Screen						
	VISIT WINDOW (\pmdays)		-14				$\pm 7^l$	$\pm 7^l$
Bile for metabolite (Part 2 PK/PD expansion cohort only) – at least 4 subjects)					Day 15			
Plasma for 4 β -hydroxycholesterol and cholesterol assay (Part 2 PK/PD expansion cohort only)			X (Day 1 prior to First Dose)			X		
Disease Assessments for Lymphoma Subjects: Baseline disease assessments at screening and repeated 8 weeks after dosing is initiated and every 12 weeks thereafter								
Computed Tomography (CT) ^k	Must be completed within 4 weeks of first dose of GSK2816126 and repeated 8 weeks after dosing is initiated. Every 12 weeks thereafter	X					X	X ^d

	STUDY PHASE	SCREEN	First Treatment Period Cycle 1			Day 21	Continuation Phase Cycle 2 and beyond	Follow-Up ^j
			Day 1 and 4 ^a	Day 8 and 11 ^a	Day 15 and 18 ^a			
	VISIT	Screen						
	VISIT WINDOW (\pmdays)	-14					$\pm 7^l$	$\pm 7^l$
Positron emission tomography (PET)	The use of standalone PET or PET in combination with CT scan is optional. Standalone PET does not replace CT	X ^e					X ^e	X ^{d,e}
Bone Marrow biopsy	See Section 7.7	X					X ^f	X ^f
B symptoms	See Section 7.7	X	X	X	X	X	X	
Disease Assessments for Multiple Myeloma (MM) subjects: Baseline disease assessments at screening, week 4 and then every 6 weeks thereafter unless otherwise noted								
Disease Characteristics	Every 6 weeks after Wk4, Including cytogenetics as appropriate	X					X	
Total Protein, CRP, β 2 microglobulin	Every 6 weeks after Wk4	X					X	
Response Assessment	Every 6 weeks after Wk4; Response criteria in Appendix 6						X	

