 - the difference between involved and uninvolved free light chain levels (absolute increase must be > 10 mg/dl): only for subjects without measurable serum and urine M-protein levels, or
 - bone marrow plasma cell percentage (the absolute % must be $\geq 10\%$) – only for subjects without measurable serum and urine M-protein levels and without measurable disease by FLC level.
 - definite development of new bone lesions or soft tissue plasmacytomas or definite increase in the size of existing bone lesions or soft tissue plasmacytomas.
 - development of hypercalcemia (corrected calcium > 11.5 mg/dl or 2.65 mmol/l) that can be attributed solely to the plasma cell proliferative disorder.
- a. All response categories (CR, sCR, VGPR, PR, MR and Progressive Disease) require two consecutive assessments made at any time before the institution of any new therapy; CR, sCR, VGPR, PR, MR, and SD categories also require no known evidence of progressive or new bone lesions if radiographic studies were performed. VGPR and CR categories require serum and urine studies regardless of whether disease at baseline was measurable on serum, urine, both, or neither. Radiographic studies are not required to satisfy these response requirements. Bone marrow assessments need not be confirmed. For Progressive Disease, serum M-component increases of more than or equal to 1 g/dL are sufficient to define relapse if starting M-component is ≥ 5 g/dL.
- b. Clarifications to IMWG criteria for coding CR and VGPR in subjects in whom the only measurable disease is by serum FLC levels: CR in such subjects indicates a normal FLC ratio of 0.26 to 1.65 in addition to CR criteria listed above. VGPR in

such subjects requires a > 90% decrease in the difference between involved and unininvolved FLC levels.

- c. Clarifications to IMWG criteria for coding Progressive Disease: Bone marrow criteria for Progressive Disease are to be used only in subjects without measurable disease by M protein and by FLC levels; “25% increase” refers to M protein, FLC, and bone marrow results, and does not refer to bone lesions, soft tissue plasmacytomas, or hypercalcemia and the “lowest response value” does not need to be a confirmed value.

References

Durie BGM, Harousseau J-L, Miguel JS, et. al. International uniform response criteria for multiple myeloma. Leukemia, 2006;20: 1467-73.

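### The protocol schedules no myeloma disease assessment at the follow-up visit, so a response or progression first seen just before treatment stops may stay unconfirmed under Appendix 6

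*Protocol*

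**What the plan says.** Section 7.7 sets the schedule by disease. For lymphoma, scans after the first are "every 12 weeks thereafter, and at the final study visit". For solid tumors, assessment is "repeated every 8 weeks after dosing is initiated, and at the final study visit". The MM bullet stops earlier: "Disease assessment for MM will be completed within 4 weeks of first dose of GSK2816126, week 4 and repeated every 6 weeks thereafter".

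Table 6 (Section 7.1) agrees with the MM bullet. Its MM block is headed "Baseline disease assessments at screening, week 4 and then every 6 weeks thereafter unless otherwise noted", and none of its rows has an entry in the Follow-Up column. The CT, PET and PSA rows do.

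Section 6.3 says that all subjects who discontinue treatment "will have safety/disease assessments at the post study treatment Follow Up Visit as specified in the Time and Events Tables".

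Appendix 6, note a, says that the MM response categories and Progressive Disease "require two consecutive assessments made at any time before the institution of any new therapy". It sets no minimum interval between the two.

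Section 2.2 makes overall response rate the primary endpoint of the MM cohort and PFS and DoR secondary. Section 12.3.5.4 censors PFS at the last adequate assessment when there is no documented event date, and leaves further censoring rules to the Reporting and Analysis Plan (RAP).

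**The concern.** Section 6.3 promises every discontinuing subject a disease assessment at follow-up but delegates its content to a table that lists none for MM. MM is also the disease whose criteria require a second reading for progression as well as for response.

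If treatment stops soon after a first qualifying reading, no later scheduled visit supplies the second one. A first partial response could then be scored as non-response in the primary analysis. A first progressive reading could be left without the confirmation that Appendix 6 asks for. An analysis plan cannot supply a measurement that was never taken, so the schedule is for the protocol to settle.

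**Working it through.** **The plan's own figure.** An exact binomial recursion over the Table 18 futility boundaries (n = 14 to 40, success if more than 6 of 40 respond) gives:

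| True rate | Quantity | Stated | Recomputed |
|---|---|---|---|
| 10% | Type I error | 0.072 | 0.0721 |
| 10% | Early termination | 89.0% | 89.0% |
| 10% | Expected N | 20.82 | 20.82 |
| 25% | Power | 0.814 | 0.8142 |
| 25% | Early termination | 16.7% | 16.7% |
| 25% | Expected N | 36.56 | 36.56 |

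The MM design figures are right, and nothing below changes them.

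**The three places side by side.**
- Section 6.3: disease assessment at follow-up for everyone who discontinues, with content taken from Table 6.
- Table 6: no MM disease assessment in the Follow-Up column.
- Section 7.7: no final-visit assessment for MM. The gap therefore appears in the prose as well as the table.

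Section 7.7 also has a withdrawal rule that is not limited by tumor type. Its trigger is a last radiographic assessment more than 8 weeks earlier, which fits poorly with a disease followed mainly by M-protein and free light chains at 6-week intervals.

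**Timing.** Inputs: MM assessments 6 × 7 = 42 days apart, window ±7 (Section 7.7); follow-up 30 days after last dose, window ±7 (Table 6, footnote j and column heading). Let g be the days from the last MM assessment to the last dose, counting that assessment as day 0.
- Follow-up falls on day g + 30, and the next MM assessment on day 42.
- Follow-up comes first when g + 30 < 42, that is, when g < 12.

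| g | Follow-up, nominal (window) | Next MM assessment, nominal (window) |
|---|---|---|
| 0 | 30 (23–37) | 42 (35–49) |
| 7 | 37 (30–44) | 42 (35–49) |
| 12 | 42 (35–49) | 42 (35–49) |

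The windows overlap even at g = 0 (days 35 to 37), so a site could combine the two, but nothing tells it to. The 12-day limit also assumes that the 6-weekly calendar continues after the last dose. Table 6 places those assessments in the continuation phase, so this is the more favorable reading.

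**Who is exposed.** An MM subject must have a first partial response or first progressive reading, stop treatment shortly afterwards, and have no unscheduled repeat before new therapy. The documents give no rate for this.

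**Effect per subject.** One unconfirmed responder lowers the observed response rate by 1/40 = 2.5 percentage points in a full cohort, or 1/14 = 7.1 points at the first futility look. It changes a decision only if the count then falls to a Table 18 boundary, for example from 7 to 6 of 40.

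**The case against.** The strongest reply is that the protocol usually secures confirmation during treatment. Section 6.3 continues treatment until progression, and under Appendix 6 a single progressive value is not yet Progressive Disease. A subject may therefore remain on treatment until the next 6-weekly reading. Confirmation also needs no scheduled visit, because any repeat before new therapy counts. Both points stand, and they limit the exposed group to those who stop early, for example for toxicity or by withdrawal, and have no repeat.

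Second, the PFS definition in Section 12.3.5.4 accepts clinical or radiological progression or death and does not mention confirmation. How an unconfirmed MM progression is handled may be settled in the RAP. This also stands, so the effect on PFS and DoR is possible but not established.

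Third, MM is not the only disease with a gap. Footnote d of Table 6 asks for lymphoma and solid-tumor follow-up scans only when the last response scan was at least 8 weeks earlier. That is correct. What distinguishes MM is that it has no follow-up entry at all.

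None of this removes the mismatch between Section 6.3 and the MM schedule.

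**Conclusion.** The inconsistency is real but modest. Section 6.3 promises a follow-up disease assessment that Section 7.7 and Table 6 do not provide for MM, where both response and progression need two consecutive readings. Subjects who stop soon after a first qualifying reading and have no repeat before new therapy may be left unconfirmed, with possible effects on the primary response rate and on secondary PFS and DoR.

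A reader might infer three stronger claims, none of which the documents support:
- **That the typical MM progression is unconfirmed.** A subject may stay on treatment to the next reading, and an unscheduled repeat is enough.
- **That PFS or DoR events are lost.** The PFS and DoR definitions do not require confirmation, and the detailed censoring rules are left to the RAP.
- **That the MM cohort has less power than stated.** The 0.814 reproduces. The 25% alternative concerns responses counted under the protocol's response criteria, which already include the two-assessment rule. Any reduction would need an assumed share of unconfirmed responders, and the documents give none.

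The conclusion rests on nominal visit dates and on reading the absence of MM Follow-Up entries as intended. The number of subjects affected is unknown.

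**What to change.** Reconcile Section 7.7 and Table 6 with Section 6.3:
- Give the MM bullet in Section 7.7 the same final-visit clause as the lymphoma and solid-tumor bullets.
- In Table 6, mark the Follow-Up column for the serum M-protein, free light chain and immunoglobulin row and for the response-assessment row. Mark urine M-protein for subjects with paraprotein in the urine.
- Limit these entries to subjects who have not started new therapy. Appendix 6 already accepts such a value as a second assessment, so no new confirmation rule is needed.

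The cost is a few routine laboratory tests for up to about 40 subjects, at a visit where Table 6 already requires chemistry and hematology samples. Appendix 6 does not require bone marrow findings to be confirmed, so this change adds no marrow procedure.
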